12.2.2 Display of adverse events

Table 12.2.2.1 Summary of adverse events.

Category	Arm A	Arm B
	N (%)	N (%)
Patients with at least one AE regardless relationship		
Any treatment-related AE		
Any grade 3/4 AE		
Any grade 3/4 treatment-related AE		
Any SAE in DB		
Any treatment-related SAE		
Any grade 3/4 SAE		
Any grade 3/4 treatment-related SAE		
AEs leading to death		
AEs treatment-related leading to death		
AEs leading to dose delay		
AEs leading to dose reduction		
AEs leading to treatment discontinuation		
AEs treatment-related leading to treatment discontinuation		

Events with onset date after crossover will be excluded

Table 12.2.2.2 Evolution of myeloma-related AEs at baseline

	Arm A		Worst grade per patient						Total		
			0		1		...				
			N	%	N	%	N	%	N	%	
Baseline	Fatigue	Grade 0									
		Grade 1									
										
	Bone Pain	Grade 0									
		Grade 1									
										
	Myopathy	Grade 0									
		Grade 1									
										
										
	Arm B										
	Fatigue	Grade 0									
Grade 1											
.....											
Bone Pain	Grade 0										
	Grade 1										
										
Myopathy	Grade 0										
	Grade 1										
										

Events with onset date after crossover will be excluded

Table 12.2.2.3 Treatment-related adverse events. Worst grade by patient

SOC	Preferred Term	Arm A								Arm B							
		Grade 1		...	Grade 4		All*		Grade 1		...	Grade 4		All*			
		N	%	...	N	%	N	%	N	%	...	N	%	N	%		
Blood and lymphatic system disorders	Anemia NOS																
	Diarrhea NOS																
	...																
Cardiac disorders	Arrhythmia NOS																
	...																

(*) Any grade. Events with onset date after crossover will be excluded

Table 12.2.2.4 Treatment-related adverse events. Worst grade by cycle

SOC	Preferred Term	Arm A								Arm B							
		Grade 1		...	Grade 4		All*		Grade 1		...	Grade 4		All*			
		N	%	...	N	%	N	%	N	%	...	N	%	N	%		
Blood and lymphatic system disorders	Anemia NOS																
	Diarrhea NOS																
	...																
Cardiac disorders	Arrhythmia NOS																
	...																

* Any grade. Events with onset date after crossover will be excluded

Table 12.2.2.5 Treatment-related adverse events in “All Crossover Patients” population. Worst grade by patient

SOC	Preferred Term	Before crossover								After crossover*										
		Grade 1				Grade 4				Grade 1				Grade 4						
		N	%	N	%	N	%	N	%			
Blood and lymphatic system disorders	Anemia NOS																			
	Diarrhea NOS																			
	...																			
Cardiac disorders	Arrhythmia NOS																			
	...																			

(*)All events with onset date ≥ administration date after crossover (**) Any grade

Table 12.2.2.6 Adverse Events regardless of relationship. Worst grade by patient

SOC	Preferred Term	Arm A								Arm B										
		Grade 1				Grade 4				Grade 1				Grade 4						
		N	%	N	%	N	%	N	%			
Blood and lymphatic system disorders	Anemia NOS																			
	Diarrhea NOS																			
	...																			
Cardiac disorders	Arrhythmia NOS																			
	...																			

(*) Any grade. Events with onset date after crossover will be excluded

Table 12.2.2.7 Adverse Events regardless of relationship. Worst grade by cycle

SOC	Preferred Term	Arm A								Arm B										
		Grade 1				Grade 4				Grade 1				Grade 4						
		N	%	N	%	N	%	N	%			
Blood and lymphatic system disorders	Anemia NOS																			
	Diarrhea NOS																			
	...																			
Cardiac disorders	Arrhythmia NOS																			
	...																			

(*) Any grade. Events with onset date after crossover will be excluded

Table 12.2.2.8 Adverse Events regardless of relationship in “All Crossover Patients” population. Worst grade by patient

SOC	Preferred Term	Before crossover								After crossover*										
		Grade 1				Grade 4				Grade 1				Grade 4						
		N	%	N	%	N	%	N	%			
Blood and lymphatic system disorders	Anemia NOS																			
	Diarrhea NOS																			
	...																			
Cardiac disorders	Arrhythmia NOS																			
	...																			

(*)All events with onset date ≥ administration date after crossover (**) Any grade.

Listing 12.2.2.9 Treatment-related grade 3-4 adverse events. Worst grade by patient

Arm	Patient id.	SOC Name	Preferred term	Grade
...				

Events with onset date after crossover will be excluded

Listing 12.2.2.10 Treatment-related grade 3-4 adverse events. Worst grade by cycle

Arm	Patient id.	Cycle	SOC Name	Preferred term	Grade
...					

Events with onset date after crossover will be excluded

Listing 12.2.2.11 Adverse Events grade 3-4 regardless of relationship. Worst grade by patient

Arm	Patient id.	SOC Name	Preferred term	Grade
...				

Events with onset date after crossover will be excluded

Listing 12.2.2.12 Adverse Events grade 3-4 regardless of relationship. Worst grade by cycle

Arm	Patient id.	Cycle	SOC Name	Preferred term	Grade
...					

Events with onset date after crossover will be excluded

Listing 12.2.2.13 Treatment-related grade 3-4 adverse events in “All Crossover Patients” population. Worst grade by patient

Arm	Patient id.	SOC Name	Preferred term	Grade
...				

Listing 12.2.2.14 Adverse Events grade 3-4 regardless of relationship in “All Crossover Patients” population. Worst grade by patient

Arm	Patient id.	SOC Name	Preferred term	Grade
...				

At the time of the analysis, if appropriate, grouping of similar or clinically related items will be made.

12.3 Serious Adverse Events and deaths.

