9.1.2 Serious Adverse Event (SAE)

A Serious Adverse Event (SAE) is any adverse experience occurring at any dose that:

- Results in death (is fatal),
- Is life-threatening,
- Requires or prolongs inpatient hospitalization,
- Results in persistent or significant disability or incapacity,

- Is a congenital anomaly or birth defect, or
- Is medically significant.
- Is any suspected transmission of an infectious agent via a medicinal product.

Medical and scientific judgment should be exercised in deciding whether expedited reporting is appropriate in other situations such as an important medical event that may not be immediately life-threatening or result in hospitalization but may jeopardize the patient or may require intervention to prevent one of the outcomes listed in the above definition.

9.1.2.1 *Death*

Death as such is the outcome of a SAE and should not be used as the SAE term itself. Instead, the cause of death should be recorded as the SAE term. When available, the autopsy report will be provided to the Sponsor.

Grade 5 should be used for events which lead immediately and directly to death, and grade 4 should be used with outcome death for events which lead to death after a longer time period, and that may also be linked to additional morbidities.

9.1.2.2 *Life Threatening Event*

Any event in which the patient was at risk of death at the time of the event; it does not refer to an event which hypothetically might have caused death if it were more severe.

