12.7 Safety analysis in special subgroups

Table 12.7.1 Worst grade 3-4 by patient in special subgroups (Gender)

Events	Arm A						Arm B					
	Male			Female			Male			Female		
	N	Grade 3-4	%	N	Grade 3-4	%	N	Grade 3-4	%	N	Grade 3-4	%
Thrombocytopenia												
Neutropenia												
AP												
Total bilirubin												
AST												
ALT												
CPK												
Nausea												
Vomiting												
Fatigue												
Other*												

(*)Any treatment-related toxicity present in >=5% of patients in any group

Table 12.7.2 Worst grade 3-4 by patient in special subgroups (Age)

Events	Arm A						Arm B					
	<65 years old			...**			<65 years old			...**		
	N	Grade 3-4	%	N	Grade 3-4	%	N	Grade 3-4	%	N	Grade 3-4	%
Thrombocytopenia												
Neutropenia												
AP												
Total bilirubin												
AST												
ALT												
CPK												
Nausea												
Vomiting												
Fatigue												
Other*												

(*)Any treatment-related toxicity present in $\geq 5\%$ of patients in any group

(**) Age 65-74, Age 75-84, Age ≥ 85 . If there is a group of age with less than 5% of patients, it could be join with the previous/next group of age.

Table 12.7.3 Worst grade 3-4 by patient in special subgroups (BMI)

Events	Arm A						Arm B					
	<30			≥ 30			<30			≥ 30		
	N	Grade 3-4	%	N	Grade 3-4	%	N	Grade 3-4	%	N	Grade 3-4	%
Thrombocytopenia												
Neutropenia												
AP												
Total bilirubin												
AST												
ALT												
CPK												
Nausea												
Vomiting												
Fatigue												
Other*												

(*)Any treatment-related toxicity present in $\geq 5\%$ of patients in any group

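### Severe-AE displays are limited to grades 3 and 4, so a patient whose worst grade for a term is 5 falls out of that term's severe count, and fatal AEs are not shown by sex, age or BMI

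*SAP*

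**What the plan says.** **Grading.** Protocol 9.1.2.1 states: "Grade 5 should be used for events which lead immediately and directly to death". The same sentence assigns grade 4, with death as the outcome, to events that prove fatal after a longer interval. SAP 7.1 and 12.2.1 describe each toxicity at its worst grade.

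**Summary table.** SAP Table 12.2.2.1 has four severe rows: "Any grade 3/4 AE", "Any grade 3/4 treatment-related AE", "Any grade 3/4 SAE" and the treatment-related version of the last. Two separate rows count AEs that led to death, overall and treatment-related.

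**Event-level tables.** The shells by system organ class and preferred term, such as "Table 12.2.2.3 Treatment-related adverse events. Worst grade by patient" and "Table 12.2.2.6 Adverse Events regardless of relationship. Worst grade by patient", run from Grade 1 to Grade 4. An any-grade column follows. It is legible in Tables 12.2.2.3 and 12.2.2.4; in the text available, Tables 12.2.2.5 to 12.2.2.8 keep only its footnote.

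**Listings.** Listings 12.2.2.9 to 12.2.2.14 are restricted to grade 3-4, for example "Listing 12.2.2.11 Adverse Events grade 3-4 regardless of relationship. Worst grade by patient".

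**Subgroups.** Tables 12.7.1 (sex), 12.7.2 (age) and 12.7.3 (BMI) report grade 3-4 only. The title of the age table reads "Worst grade 3-4 by patient in special subgroups (Age". None has a row for grade 5 or death.

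**The concern.** Readers usually take a severe-toxicity rate to mean grade 3 or worse. Here the worst possible grade is outside the count. The cut also splits fatal events by speed of death: a slower death is coded grade 4 and counts as severe, while an immediate one is coded grade 5 and does not. Nothing in the SAP explains that ordering.

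Comparing safety between the arms is a secondary objective (Protocol 2.2, SAP 3.2). Safety by age was extended in SAP version 4.0, with reference to a geriatric-studies guideline, yet the age table is one of those that leaves out the gravest outcome.

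**Working it through.** No figure in the plan depends on this point, so there is nothing to reproduce. The check is to follow each kind of patient through the shells, read literally.

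| Patient | Summary rows for grade 3/4 (Table 12.2.2.1) | Grade columns for the term (Tables 12.2.2.3-8) | Grade 3-4 listings and Tables 12.7.1-3, that term |
|---|---|---|---|
| Worst grade for the term is 3 or 4, not fatal | counted | counted | counted |
| Slower fatal event, coded grade 4 | counted | counted under Grade 4 | counted |
| Immediately fatal event, grade 5, plus another qualifying grade 3/4 event | counted, through the other event | any-grade column only | missing for the fatal term |
| Immediately fatal event, grade 5, no other qualifying grade 3/4 event | missing | any-grade column only | missing for the fatal term |

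Qualifying means that the other event meets the row's own condition, such as being treatment-related or serious. In the subgroup tables, the last column applies only if the term has a row.

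**Can the reader rebuild a grade 3-or-higher rate from Table 12.2.2.1?** Only if the overlap is known:

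patients with grade ≥3 = (patients with any grade 3/4) + (patients with a fatal AE) − (patients in both)

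Slower deaths coded grade 4 fall in both rows, and so do grade 5 patients who had another grade 3/4 event. The table does not report the overlap, so adding the two rows gives only an upper limit.

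**Size, for illustration.** Planned arm sizes are 167 and 83 (SAP 5.2). The safety set is treated patients (SAP 4.3), so the real denominators may differ.

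- One patient: 1/167 = 0.6 points in Arm A; 1/83 = 1.2 points in Arm B.
- Assumed grade 5 share of 1% in both arms: 0.01 × 167 = 1.67, about 2 patients; 0.01 × 83 = 0.83, about 1 patient.
- Assumed 5% in Arm A and 2% in Arm B: 0.05 × 167 = 8.35, about 8 patients (8/167 = 4.8 points); 0.02 × 83 = 1.66, about 2 patients (2/83 = 2.4 points).
- Assumed 5% in both arms: about 8 patients (4.8 points) and 0.05 × 83 = 4.15, about 4 patients (4/83 = 4.8 points).

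These totals are spread over the terms concerned. In the any-grade-3/4 summary row the loss lies between 0 (every such patient had another grade 3/4 event) and the full number (none did).

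**Age bands.** Under the footnote to Table 12.7.2, bands holding less than 5% of patients may be merged. If a band held 5% of each planned arm, about 8 and 4 patients, one patient would be 1/8 = 12.5 points in Arm A and 1/4 = 25 points in Arm B.

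**The case against.** The strongest reply is that fatal AEs are reported elsewhere and that showing non-fatal severe events beside fatal ones is a matter of presentation. Much of this stands.

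- **Deaths are not hidden.** A reader might infer from the grade cut that they are. The documents do not support that. Fatal AEs appear in the two death rows of Table 12.2.2.1, in the any-grade columns, in the summaries by outcome and by relationship promised in SAP 7.1, in Table 12.3.2.1, and event by event with preferred term and grade in Listings 12.3.1.1 and 12.3.2.3. An arm-level excess of fatal toxicity would be seen.
- **A grade 5 event does not always remove a patient from a severe row.** A reader might assume that it does. The rows of Table 12.2.2.1 are any-event rows, so the loss there can be zero. It follows directly only for the affected term in the worst-grade displays.
- **Only part of the fatal events is affected.** Those coded grade 4 with outcome death stay in.
- **The subgroup rows are mostly unlikely to reach grade 5.** Seven of the ten named rows are laboratory items; the others are nausea, vomiting and fatigue. The remaining row admits only treatment-related toxicities seen in at least 5% of patients in a group, so a rare fatal event might have no row under any grade cut.
- **Not every worst-grade table stops at grade 4.** Table 12.2.2.2 leaves its upper grade open.

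What the reply does not answer is that no planned table gives fatal AEs by sex, age or BMI, and that the summary rows cannot be combined into a grade 3-or-higher rate. The last objection about subgroup rows also shows that changing the grade cut alone would not be enough there.

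**Conclusion.** The point holds as a minor one. Read literally, the grade 3-4 displays leave out a patient whose worst grade for a term is 5, while slower deaths coded grade 4 are counted. In the summary rows the patient is lost only without another qualifying grade 3/4 event. Fatal AEs can be seen for the whole study but not by subgroup.

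The size is unknown, because the documents give no grade 5 rate. The percentages above are illustrations on planned arm sizes. A reader might go further and conclude that severe toxicity will be understated most in older patients or in the arm with more deaths. The documents give no grade 5 counts by arm or age, so that direction is possible but not shown. The planned efficacy analyses do not use these displays.

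**What to change.** 1. In Table 12.2.2.1, Listings 12.2.2.9 to 12.2.2.14 and Tables 12.7.1 to 12.7.3, replace the grade 3/4 and grade 3-4 wording by grade 3 or higher.
2. Add a grade 5 column to Tables 12.2.2.3 to 12.2.2.8.
3. Add to Tables 12.7.1 to 12.7.3 a row for patients with an AE leading to death, so that a fatal event is shown by sex, age and BMI even when its term has no row of its own.

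Keep the existing death rows and listings. The cost is table-shell edits; grade, outcome and the subgroup variables are already planned for collection or reporting, so no new data are needed.

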1.3.4.2.6 Constitutional Symptoms

Asthenia was the constitutional AE most frequently found in patients in phase II studies with single-agent plitidepsin. A total of 31% of patients treated with the 1-hour infusion had asthenia, with 8% of cases being grade 3-4. However, its significance may be confounded, since the underlying malignancy is frequently a cause of asthenia in cancer patients.

Other severe AEs reported within this schedule were grade 3 edema in one patient (1%) and pyrexia also in one (1%) patient. Mild grade 1-2 pyrexia was reported in other schedules, particularly in the 3-hour i.v. infusion every two weeks (69% of patients). It was usually associated with shivering and developed within 24 hours after the start of the infusion.

One patient had multi-organ failure and died, most likely as a consequence of the underlying disease.

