9.2.1 Reporting of Adverse Events

The Sponsor will collect AEs until 30 days after administration of the last dose of study drug(s) or until the start of a new antitumor therapy, whichever occurs first. All AEs suspected to be related to study drug(s) must be followed after the time of therapy discontinuation until the event or its sequelae resolve or stabilize at an acceptable level to the Investigator and the Sponsor.

All AEs, including misuse, overdose and abuse must be recorded using medical terminology in the source document and the CRF. Whenever possible the Investigator will record the main diagnosis instead of the signs and symptoms normally included in the diagnoses.

Investigators must assess severity (grade) of the event following NCI-CTCAE v. 4 and assign relationship to each study drug; pursue and obtain information adequate both to determine the outcome and to assess whether it meets the criteria for classification as a SAE requiring immediate notification to PharmaMar or its designated representative. The Investigator must provide any relevant information as requested by the Sponsor in addition to that on the CRF.

Abnormal laboratory tests occurring during the study are AEs, but they should be collected only in the AE section of the CRF in some cases:

- Is associated with clinically significant symptoms, and/or
- Leads to a change in study dosing or discontinuation from the study, significant additional concomitant drug treatment or other therapy, and/or
- Leads to any of the outcomes included in the definition of a SAE.
- The test result is considered to be a clinically relevant by the Investigator.

Otherwise laboratory results should be reported in the corresponding section of the CRF (e.g. biochemistry, hematology).

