7 STATISTICAL METHODOLOGY FOR SAFETY

Patients are evaluable for general safety if they received any study treatment. Safety will be evaluated in each arm separately according to the actual treatment received.

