12.1 Extent of exposure

12.1.1 Treatment administration

Table 12.1.1.1 Number of cycles administered and dose intensity

No. of cycles administered per patient	Arm A		Arm B	
	N	%	N	%
1				
2				
3				
...				
Median (range)				
Time on treatment (weeks)				
Median				
Range				
Plitidepsin cumulative dose (mg/m ²)			NA	
Median				
Range				
Plitidepsin dose intensity (mg/m ² /wk)			NA	
Median				
Range				
Plitidepsin relative dose intensity (%)			NA	
Median				
Range				
Dexamethasone cumulative dose (mg)				
Median				
Range				
Dexamethasone dose intensity (mg/wk)				
Median				
Range				
Dexamethasone relative dose intensity (%)				
Median				
Range				

NA: Not applicable. Cycles after crossover will be excluded.

Table 12.1.1.2 Number of cycles administered and dose intensity after crossover

No. of cycles administered per patient	After crossover	
	N	%
1		
2		
3		
...		
Median (range)		
Time on treatment (weeks)		
Median		
Range		
Plitidepsin cumulative dose (mg/m ²)		
Median		
Range		
Plitidepsin dose intensity (mg/m ² /wk)		
Median		
Range		
Plitidepsin relative dose intensity (%)		
Median		
Range		
Dexamethasone cumulative dose (mg)		
Median		
Range		
Dexamethasone dose intensity (mg/wk)		
Median		
Range		
Dexamethasone relative dose intensity (%)		
Median		
Range		

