12.2 Adverse Events (AEs)

12.2.1 Adverse events

As far as all the toxicities are concerned, the NCI-CTC grade will be used wherever an NCI-CTC grading exists. Otherwise, the severity will be noted. As a convention, the term «Grade» will always be used. Toxicities will be described according to the worst NCI-CTC grade or, for toxicities which do not form the subject of NCI-CTC classification, according to the worst severity.

In this section the adverse events will be described and different tables will be created for events related to treatment (stated as related to at least one of the two trial medications or unknown relationship). In case of a high frequency of adverse events attributable only to one of the investigational drugs, all tables in this section will be duplicated to show adverse events related to plitidepsin or dexamethasone (i.e. table 12.2.2.2, additional tables 12.2.2.2p and 12.2.2.2d).

Type of toxicity and worst grade or severity by cycle and by patient will be summarized according to the Preferred Term coded with MedDRA. Tables will be organized per category of events using System Organ Class of MedDRA.

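### The main adverse event tables remove post-crossover toxicity from Arm B by onset date alone but report worst grade, so an event that worsens after plitidepsin is added can be shown as dexamethasone-alone toxicity

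*SAP*

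**What the plan says.** SAP section 12.2.2 sets out the adverse event comparison between arms. Tables 12.2.2.1 to 12.2.2.4, 12.2.2.6 and 12.2.2.7, and Listings 12.2.2.9 to 12.2.2.12, carry the footnote "Events with onset date after crossover will be excluded". It does not say which date stands for crossover, or whether that date itself counts as after.

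Tables 12.2.2.5 and 12.2.2.8 show crossover patients before and after the switch. Their after-crossover column has an explicit boundary: "All events with onset date ≥ administration date after crossover".

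On what is tabulated, SAP section 12.2.1 says: "Type of toxicity and worst grade or severity by cycle and by patient will be summarized according to the Preferred Term coded with MedDRA". On attribution, SAP section 7 says: "Safety will be evaluated in each arm separately according to the actual treatment received". SAP section 8.2 treats a crossover patient as on treatment through both phases. The exposure tables in section 12.1 use a different filter: "Cycles after crossover will be excluded".

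**The concern.** The filter acts on when an event started, while the tables report how bad it became. For an event that spans crossover these belong to different treatments. An onset filter cannot remove a grade reached on plitidepsin plus dexamethasone if the record carries an onset date from the dexamethasone-alone phase.

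Comparing the safety profile of the two arms is a stated secondary objective. Any misplacement of this kind runs in one direction: it adds toxicity to the control arm and makes plitidepsin look less toxic by comparison. In the before/after tables it also takes the worsening out of the column meant to show the effect of adding plitidepsin.

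**Working it through.** The documents give no figure on this point, so there is none to reproduce. The check follows each type of event in an Arm B patient who crosses over.

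| Event | Arm B column, main tables | After-crossover column, Tables 12.2.2.5 and 12.2.2.8 |
|---|---|---|
| Starts and peaks before crossover | Counted, correctly | Not counted, correctly |
| Starts on a later date than the first combination dose | Excluded, correctly | Counted, correctly |
| Starts at grade 1 before, reaches grade 3 after, one record | Kept, at grade 3 | Missing |
| Same course, worsening entered as a new record with its own onset date | New record excluded, correctly | Counted, correctly |
| Starts on the date of the first combination dose | Kept if after is read strictly and crossover is dated at that dose; otherwise excluded | Counted |

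**Worsening.** Rows three and four differ only in how a grade increase is recorded. Protocol section 9.2.1 says: "Investigators must assess severity (grade) of the event following NCI-CTCAE v. 4 and assign relationship to each study drug". It does not say whether a worsening opens a new record, and the SAP does not either.

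Table 12.2.2.2 is the clearest case. It sets baseline grade against worst grade for fatigue, bone pain and myopathy. Patients in its rows of grade 1 or higher had the symptom before any study drug, so if the worsening stays on that record, the onset filter cannot act. Muscular events are described in Protocol section 1.3.4.2.1 as plitidepsin's main dose-limiting toxicity, so the myopathy rows are the ones most exposed. The by-cycle Tables 12.2.2.4 and 12.2.2.7 have the same gap: they carry the onset footnote but not the cycle exclusion of the exposure tables.

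**First combination day.** Row five is a mismatch between two footnotes. Under a strict reading the same event appears in Arm B and after crossover.

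**Size.** Inputs: Arm B is approximately 83 patients (Protocol section 10.1), and the number crossing over is described only as indeterminate (SAP section 6.2.3).

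- One misplaced patient: 100 × 1/83 = 1.2 percentage points.
- In general: inflation in points = 100 × c × q, where c is the share of Arm B that crosses over and q is the share of those with a misplaced event. Both are assumed.

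| | c = 25% | c = 50% | c = 75% |
|---|---|---|---|
| q = 5% | 1.25 | 2.5 | 3.75 |
| q = 20% | 5 | 10 | 15 |

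A worsening event changes the incidence at the higher grade. It leaves the any-grade total unchanged, because the patient was already counted. A same-day event raises the any-grade total only if the patient did not have that term before.

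**The case against.** The best reply on the first-day issue is that the SAP has only one explicit definition of after crossover for adverse events, and it includes the day of the first combination dose. The revision history supports reading the main footnote the same way: the on-or-after rule was already in the crossover tables when the main footnote was added in the change from v3.0 to v4.0. Section 7 points in the same direction. This largely stands, and it reduces the first-day issue to inconsistent wording.

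On worsening, the reply is that the documents never say a grade increase keeps the early onset date. If it opens a new record, the footnote already works. The by-cycle tables suggest that grades over time are available. This stands as a condition on the point, but it does not remove it: no document states the recording rule, and the SAP should not depend on an unstated one.

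A third reply is that causality is assigned to each drug, so a plitidepsin-related event in the dexamethasone-alone column would be noticed. That helps only in part. Section 12.2.1 plans tables split by drug only if events attributable to a single drug are frequent, and they would be added to the main tables. Tables 12.2.2.6 and 12.2.2.7 ignore causality altogether.

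The tables are also descriptive. That limits the consequence, but they are the evidence for the safety comparison.

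**Conclusion.** The point holds in a conditional form. The main outputs filter Arm B by onset date while reporting worst grade, and no rule covers an event ongoing at crossover. If worsening is kept on the original record, combination-phase grades enter the dexamethasone-alone column and are lost from the after-crossover column. The first-day issue is a secondary mismatch of wording.

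The size cannot be derived. It is about 1.2 points per misplaced patient, and the total could be near zero or material depending on the crossover share and the recording convention.

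A reader might go further and conclude that first-infusion-day reactions are in fact counted against dexamethasone alone. The documents do not support that: it needs a strict reading and a crossover date that the footnote does not give. A reader might also take the 69% pyrexia figure for the 3-hour schedule (Protocol section 1.3.4.2.6) and multiply it by a crossover share of 30% to 70% and a same-day share of 25% to 75%. That gives 0.30 × 0.69 × 0.25 = 5.2 points up to 0.70 × 0.69 × 0.75 = 36.2 points. Only the 69% is in the documents. It refers to mild, grade 1-2 pyrexia in single-agent experience, and the product ignores patients who already had pyrexia before crossover. It also concerns only the weaker, first-day issue, so it should not be used as an estimate.

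**What to change.** Replace the footnote in Tables 12.2.2.1 to 12.2.2.4, 12.2.2.6 and 12.2.2.7 and Listings 12.2.2.9 to 12.2.2.12 with: *Events with onset on or after the date of the first combination dose are excluded; an event ongoing at that date is shown at the worst grade recorded before it.* In Tables 12.2.2.5 and 12.2.2.8, count any increase in grade on or after that date in the after-crossover column.

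The laboratory outputs in section 12.4 use the same footnote. State there that samples drawn before the first combination dose count as before crossover, including those drawn on the same day.

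The cost is the footnote wording and a small programming change, using the by-cycle grades the SAP already plans to summarize. No new visits or procedures are needed. The rule gives the same result whether or not a worsening opens a new record.
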